5.7.2. Analyses of Secondary Efficacy Endpoints

Statistical Analysis:

All observed data regardless of whether rescue medication is used, or data is collected after study drug withdrawal. Descriptive statistics will be provided for categorical and continuous variables. The efficacy assessment and the related analysis methods are listed below:

Assessment	Analysis Methods
EASI	
• Mean and change from baseline in EASI at each visit through week 24• Percent change from baseline in EASI at each visit through week 24• Percent of patients with EASI-50 ($\geq 50\%$ reduction from baseline in EASI) at each visit through week 24• Percent of patients with EASI-90 ($\geq 90\%$ reduction from baseline in EASI) at each visit through week 24
IGA	
• Percent of patients with Investigator's Global Assessment (IGA) = 0 to 1 at each visit from baseline through week 24
SCORAD	
• Mean and change from baseline in total SCORAD at each visit through week 24• Percent change from baseline in total SCORAD at each visit through week 24• Percent of patients with SCORAD-50 ($\geq 50\%$ reduction in SCORAD from baseline) at each visit through week 24• Percent of patients with SCORAD-75 ($\geq 75\%$ reduction in SCORAD from baseline) at each visit through week 24• Percent of patients with SCORAD-90 ($\geq 90\%$ reduction in SCORAD from baseline) at each visit through week 24

	
• Mean and change from baseline in SCORAD Dryness component at each visit through week 24• Percent change from baseline in SCORAD Dryness component at each visit through week 24• Mean and change from baseline in SCORAD Erythema component at each visit through week 24• Percent change from baseline in SCORAD Erythema component at each visit through week 24• Mean and change from baseline in SCORAD Sleep NRS at each visit through week 24• Percent change from baseline in SCORAD Sleep NRS at each visit through week 24• Mean and change from baseline in SCORAD Pruritus NRS at each visit through week 24• Percent change from baseline in SCORAD Pruritus NRS at each visit through week 24
BSA	
• Mean and change from baseline in percent BSA at each visit through week 24• Percent change from baseline in percent BSA at each visit through week 24
PHSS	
• Overall Disease Severity: Mean and change from baseline at each visit through week 24• Overall Disease Severity: Percent change from baseline at each visit through week 24• Percent of patients in each overall disease severity grade (0-8) at each visit through week 24• Percent of patients in each category of Pigmentary Intensity of Hyperpigmented Lesions (None, Trace, Mild, Moderate, Marked, Severe) at each visit through week 24• Percent of patients in each Area of Hyperpigmented Lesions (None, Trace, Mild, Moderate, Marked, Severe) at each visit through week 24• Percent of patients in each category of Degree of Hypopigmentation (None, Trace, Mild, Moderate, Marked, Severe) at each visit through week 24

	
Percent of patients in each category of Erythema, Burning, Peeling, Dryness (None, Trace, Mild, Moderate, Marked, Severe) at each visit through week 24In the subgroup of patients with Overall Disease Severity Score ≥ 4 at baseline:
Mean and change from baseline of Overall Disease Severity at each visitPercent change from baseline of Overall Disease Severity at each visitPercent of patients with decrease of ≥ 1 point at each visitPercent of patients with decrease of ≥ 2 points at each visitPercent of patients with decrease of ≥ 3 points at each visitPercent of patients with decrease of ≥ 4 points at each visitPercent of patients achieving score of 0 at each visitPercent of patients achieving score of 0 or 1 at each visit
POEM	
Mean and change from baseline in Patient Oriented Eczema Measure (POEM) total score and item scores at each visit through week 24Percent change from baseline in Patient Oriented Eczema Measure (POEM) total score and item scores at each visit through week 24Percent of patients with ≥ 4 point Patient Oriented Eczema Measure (POEM) total score decrease from baseline at each visit through week 24
PGID	
Percent of patients in each category (None/Mild/Moderate/Severe/Very Severe) at each visit through week 24Percent of patients with “No Symptoms” or “Mild Symptoms” at each visit through week 24Percent of patients with “Moderate Symptoms” at each visit through week 24Percent of patients with “Severe Symptoms” or “Very severe Symptoms” at each visit through week 24
PGIC	
Percent of patients with Patient Global Impression of Change response as “Much better”, “Moderately better”,

	
“A Little Better”, “No Change”, “A Little Worse”, “Moderately Worse”, “Much Worse” 7 categories at each visit through week 24

Peak Pruritus NRS	
Percent of patients with improvement (reduction) of weekly average of daily PP NRS ≥ 4 from baseline at each visit through week 24Percent of patients with ≥ 3-point improvement (reduction) of weekly average of daily PP NRS from baseline at each visit through week 24Mean and change from baseline in weekly average of daily PP NRS at each visit through week 24Percent change from baseline in weekly average of daily PP NRS at each visit through week 24
Sleep Quality NRS	
Mean and change from baseline weekly average of daily Sleep Quality NRS at each visit through week 24Percent Change from baseline weekly average of daily Sleep Quality NRS at each visit through week 24
Skin Pain NRS	
Mean and change from baseline in Skin Pain NRS at each visit through week 24Percent change from baseline in Skin Pain NRS at each visit through week 24
Dyspigmentation NRS	
Skin Lightening: mean and change from baseline at each visit through week 24Skin Lightening: percent change from baseline at each visit through week 24Percent of patients bothered by skin lightening (only in patients with non-zero skin lightening score)Skin darkening: mean and change from baseline at each visit through week 24Skin darkening: percent change from baseline at each visit through week 24 
In the subgroup of patients who respond at baseline that they are either “very bothered (3)” or “extremely bothered (4)” by how their darkened skin looked because of AD:

	
○ Skin darkening: mean and change from baseline at each visit○ Skin darkening: percent change from baseline at each visit○ Percent of patients in each of the following categories at each visit:
● Not bothered at all (0)● Slightly bothered (1)● Somewhat bothered (2)● Very bothered (3)● Extremely bothered (4) 
In the subgroup of patients who respond at baseline that they are either “very bothered (3)” or “extremely bothered (4)” by how their lightened skin looked because of AD:
 
○ Skin Lightening: mean and change from baseline at each visit○ Skin Lightening: percent change from baseline at each visit○ Percent of patients in each of the following categories at each visit:
● Not bothered at all (0)● Slightly bothered (1)● Somewhat bothered (2)● Very bothered (3)● Extremely bothered (4)
Xerosis NRS	
● Skin dryness mean and change from baseline at each visit through week 24● Skin dryness percent change from baseline at each visit through week 24● Bothered by how Skin Dryness felt: (only in patients with non-zero skin dryness at baseline):
● Not bothered at all (0)● Slightly bothered (1)● Somewhat bothered (2)● Very bothered (3)

	
• Extremely bothered (4)• Bothered by how Skin Dryness looked: (only in patients with non-zero skin dryness at baseline)
• Not bothered at all (0)• Slightly bothered (1)• Somewhat bothered (2)• Very bothered (3)• Extremely bothered (4) 
In the subgroup of patients who respond at baseline that they are either “very bothered (3)” or “extremely bothered (4)” by how their dry skin felt because of AD:
 
○ Skin dryness mean and change from baseline at each visit○ Skin dryness percent change from baseline at each visit○ Percent of patients in each of the following categories at each visit:
• Not bothered at all (0)• Slightly bothered (1)• Somewhat bothered (2)• Very bothered (3)• Extremely bothered (4)
DLQI, CDLQI	
• Mean and change from baseline in Dermatology Life Quality Index (DLQI; age ≥ 16) at each visit through week 24• Percent change from baseline in Dermatology Life Quality Index (DLQI; age ≥ 16) at each visit through week 24• Percent of patients with ≥ 4-point decrease from baseline in DLQI at each visit through week 24• Mean and change from baseline in Children’s Dermatology Life Quality Index (CDLQI; age < 16) at each visit through

	
week 24
 
• Percent change from baseline in Children's Dermatology Life Quality Index (CDLQI; age <16) at each visit through week 24• Percent of patients with ≥ 4-point decrease from baseline in CDLQI at each visit through week 24
HADS	
• Mean and change from baseline in Hospital Anxiety and Depression Scale (HADS) total score, anxiety and depression sub-scores at each visit through week 24• Mean and change from baseline in Hospital Anxiety and Depression Scale (HADS) anxiety and depression sub-scores at each visit through week 24• Percent change from baseline in Hospital Anxiety and Depression Scale (HADS) total score, anxiety and depression sub-scores at each visit through week 24• Percent change from baseline in Hospital Anxiety and Depression Scale (HADS) anxiety and depression sub-scores at each visit through week 24• Percent of patients with Anxiety score < 11 among patients with baseline Anxiety score ≥ 11 at each visit through week 24• Percent of patients with Depression score < 11 among patients with baseline Depression score ≥ 11 at each visit through week 24
AD phenotypic description	
• Percent of each phenotype at baseline• Percent of phenotypes reported as dominant at baseline• For each dominant phenotype, anatomic distribution of lesions at baseline

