3.1. Full Analysis Set (FAS)

The full analysis set (FAS) includes all participants who are enrolled in the study and have baseline assessment. The FAS is the main analysis population for the study and will be used to summarize patient disposition, baseline characteristics and to analyze efficacy variables.

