5.7. Analyses of Efficacy Data

The efficacy variables will be summarized for all patients in FAS. The continuous efficacy variables will be summarized using number of patients, mean, SD, median, Q1, Q3, minimum and maximum. Categorical efficacy variables will be summarized using patient counts and percentage. No formal statistical hypothesis testing will be performed. The graph of mean value for continuous variable or proportion for categorical variable by visit will be provided.

Unless otherwise specified, all observed values, regardless of whether data is collected after withdrawal from study treatment will be used for analysis.

Unless otherwise specified, for the categorical efficacy variables, the proportion of patients with each response at each visit will be calculated using the number of patients with a non-missing value at the visit as the denominator.

Subgroup analyses for efficacy

Different subgroups within the FAS population will be defined as below. The analyses will be performed for the primary efficacy variables by:

- Duration of AD (<5 years, \geq 5 years)
- Baseline weight with grouping (\geq 60kg, <60kg for adolescents, <60 kg, \geq 60-<90 kg, \geq 90 kg for adults)
- BMI with grouping (<35, \geq 35-<40, \geq 40)
- Age (\geq 12-<18, \geq 18-<40, \geq 40-<65, \geq 65)
- Sex (Male, Female)
- Race (Black or African American, Asian, Others)
- Fitzpatrick Skin Types phototype (FST 4; FST 5 + 6 [combined])

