The baseline NRS is defined as the prorated average of the NRSs reported continuously for 7 days right before and on the baseline visit (i.e. study day -6 to day 1). For post-baseline NRS, the mean weekly NRS is calculated as the prorated average of the reported daily NRS within the week. For example, if there are 3 scores in a week, the prorated average = (score1 + score2 + score3)/3.

Body Surface Area Affected by Atopic Dermatitis

The BSA affected by AD will be assessed for each major section of the body (the possible highest score for each region is: head and neck [9%], anterior trunk [18%], back [18%], upper limbs [18%], lower limbs [36%], and genitals [1%]) and will be reported as a percentage of all major body sections combined. Patients will undergo this assessment at baseline and subsequent study visits as indicated in Section 10.2.

Dermatology Life Quality Index (DLQI)

The DLQI is a 10-item, validated questionnaire ([Badia 1999](#)) used in clinical practice and clinical trials to assess the impact of AD disease symptoms and treatment on Quality of Life (QoL). The format is a simple response to 10 items, which assess QoL over the past week. For each item, the scale is rated as follows: 0=’not at all’=’not relevant’; 1=’a little’; 2=’a lot’; 3=’very much’=’yes’ in question 7, with an overall scoring system of 0 to 30; a high score is indicative of a poor QoL. The DLQI will be assessed at time points according to in Section 10.2.

- Handling missing items from DLQI
 - i. If one question is left unanswered this is scored 0 and the scores are summed and expressed as usual out of a maximum of 30.
 - ii. If two or more questions are left unanswered the questionnaire is not scored.
 - iii. If question 7 is answered 'yes' this is scored 3 even if in the same question one of the other boxes is ticked.
 - iv. If question 7 is answered 'no' or 'not relevant' but then either 'a lot' or 'a little' is ticked this is then scored 2 or 1.
 - v. If two or more response options are ticked for one question, the response option with the highest score should be recorded.

vi. The DLQI can be analyzed by calculating the score for each of its six sub-scales. When using sub-scales, if the answer to one question in a sub-scale is missing, that sub-scale should not be scored:

Symptoms and feelings	Questions 1 and 2	Score maximum 6
Daily activities	Questions 3 and 4	Score maximum 6
Leisure	Questions 5 and 6	Score maximum 6
Work and School	Question 7	Score maximum 3

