Personal relationships	Questions 8 and 9	Score maximum 6
Treatment	Question 10	Score maximum 3

Children's Dermatology Life Quality Index (CDLQI)

The CDLQI is a validated questionnaire designed to measure the impact of skin disease on the QOL in children ≥ 4 years of age ([Lewis-Jones 1995](#)). The aim of the questionnaire is to measure how much a patient's skin problem has affected the patient over a recall period of the past week. In this study, a cartoon version of the CDLQI will be administered to patients 4 to 5 years of age, with the assistance of a parent or adult "as necessary". If assistance of parent or adult caregiver is required, it is recommended that the same person assist the patient throughout the study. The cartoon version of the CDLQI uses the same text and scoring system as the original CDLQI but includes 10 color drawings of a dog illustrating the theme of each question.

To complete the questionnaire, patients need to provide responses to 10 questions (the questions focus on domains such as symptoms feelings associated with disease, the impact of the disease on leisure, school or holidays, personal relationships, sleep, and side effects of treatment for the skin disease. The instrument has a recall period of 7 days. Nine of the 10 questions are scored as follows:

- Very much = 3
- Quite a lot = 2
- Only a little = 1
- Not at all = 0
- Question unanswered = 0

Question 7 has an additional possible response (prevented school), which is assigned a score of 3. Overall scoring ranges from 0 to 30; a high score is indicative of a poor QOL. The CDLQI will be assessed at the scheduled and unscheduled clinic visits according to Section [10.2](#).

Handling missing items from CDLQI:

- i. If one question is left unanswered this is scored 0 and the scores are summed and expressed as usual out of a maximum of 30.
- ii. If two or more questions are left unanswered the questionnaire is not scored.

- iii. If two or more response options are ticked for one question, the response option with the highest score should be recorded.
- iv. The CDLQI sub-scores may be analyzed by calculating the score for each of its six sub-scales. When using sub-scales, if the answer to one question in a sub-scale is missing, that sub-scale will not be scored:

Sub-scales	Questions	Maximum Score
Symptoms and feelings	Questions 1,2	6
Leisure	Questions 4, 5 and 6	9
School or holidays	Question 7	3
Personal relationships	Questions 3 and 8	6
Sleep	Question 9	3

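### The DLQI and CDLQI 4-point responder rates count anyone who starts at 0 to 3 as a non-responder, and the SAP does not ask how many such participants there are

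*SAP*

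**What the plan says.** The analysis table in SAP 5.7.2 gives three responder rates based on a fall of 4 points or more:

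- DLQI: the percentage with a "decrease from baseline in DLQI at each visit through week 24" of that size.
- CDLQI: the percentage with a "decrease from baseline in CDLQI at each visit through week 24" of that size.
- POEM: the percentage with a "total score decrease from baseline at each visit through week 24" of that size.

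None of the three lines carries a baseline condition. SAP 5.7 supplies the default for categorical efficacy variables: unless stated otherwise, the proportion "will be calculated using the number of patients with a non-missing value at the visit as the denominator". The analysis population does not narrow this, because the FAS in SAP 3.1 "includes all participants who are enrolled in the study and have baseline assessment".

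The inclusion criteria (protocol 7.2.1) set minimum values for EASI, IGA, BSA and weekly average peak pruritus NRS. They set none for DLQI, CDLQI or POEM.

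SAP 10.3 puts the bottom of each scale at 0. DLQI is described "with an overall scoring system of 0 to 30; a high score is indicative of a poor QoL". For CDLQI, "Overall scoring ranges from 0 to 30; a high score is indicative of a poor QOL". The POEM total runs from 0 to 28.

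**The concern.** A score of 0 to 3 cannot fall by 4. Under the SAP as written, a participant who starts there stays in the denominator at every visit and can never enter the numerator, however well the treatment works. The reported percentage then mixes two things: how often participants with room to improve do improve, and how many had little quality-of-life impact to begin with.

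The distortion can only go downward. In a single-arm descriptive study the percentage itself is the result, and no control arm shares the artefact. Quality of life is a named secondary objective (protocol 2.2), so these rates are likely to be read at face value.

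**Working it through.** **1. The plan's own figures.** The documents state no responder rate for these instruments and no baseline distribution, so there is no figure of this kind to reproduce. The only sizing figure is in protocol 11.2: 120 participants with up to 15% dropout yield about 105. Directly, 120 × (1 - 0.15) = 102; an exact 105 corresponds to 1 - 105/120 = 12.5% dropout. The two agree within the stated approximation, and nothing below depends on the difference. I use 105 only to put counts on an example. Each age-specific instrument will have fewer.

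**2. Formula.** Let r be the 4-point response rate among participants with baseline 4 or more, and q the share of the visit denominator with baseline below 4. The second group responds with probability 0, so:

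- reported rate = r × (1 - q) + 0 × q = r(1 - q)
- loss against r = r × q

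**3. Numbers.** Both r and q are assumed. At r = 70%:

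| q (assumed) | Reported rate | Loss (points) |
|---|---|---|
| 0% | 0.70 × 1.00 = 70.0% | 0 |
| 5% | 0.70 × 0.95 = 66.5% | 3.5 |
| 10% | 0.70 × 0.90 = 63.0% | 7.0 |
| 15% | 0.70 × 0.85 = 59.5% | 10.5 |

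For r anywhere from 60% to 90%, the loss is 0.6 to 0.9 points at q = 1%, 3.0 to 4.5 at q = 5%, and 6 to 9 at q = 10%. In counts: with 105 assessed, 5 of them starting below 4 and 80 responders, the restricted rate is 80/100 = 80.0% and the SAP rate is 80/105 = 76.2%.

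**4. CDLQI.** It is used only below age 16, here ages 12 to 15, so its denominator will be a fraction of the study. At an assumed r of 80%, one participant starting below 4 costs 0.80 × 1/n: 16.0 points at n = 5, 8.0 at n = 10, 5.3 at n = 15.

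**5. Can a baseline below 4 occur?** For DLQI and CDLQI, no entry criterion bounds the score. The scoring rules in SAP 10.3 can lower it: a DLQI item marked not relevant scores 0, and one unanswered item scores 0 on either instrument.

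For POEM the entry criteria bite indirectly. A weekly average peak pruritus of 4 or more over 7 daily scores needs a sum of at least 28, so itch on at least 3 days; over the minimum 4 scores it needs a sum of 16, so itch on at least 2 days. That forces only 1 or 2 points on the POEM itch item, so a total below 4 is arithmetically possible. It is implausible next to EASI ≥16 and IGA ≥3, because the bands in SAP 10.3 class a POEM of 0 to 2 as clear or almost clear and 3 as the lowest mild score.

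**6. Other point-decrease rates in the same table.** The peak pruritus rates (3 or 4 points) are protected by the entry requirement of 4 or more. The PHSS rates (1 to 4 points) are given within a subgroup with baseline score 4 or more. DLQI, CDLQI and POEM are the ones without either safeguard.

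**The case against.** Several points on the other side stand.

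- **Nothing shows that anyone starts below 4.** A reader might infer that the rates will be pulled down by several points. The documents contain no baseline data for these scales, and q = 0 is possible.
- **POEM does not deserve equal weight**, for the reason in step 5 of the working.
- **HADS is not a precedent that the SAP breaks.** A reader might infer inconsistency because HADS is reported "among patients with baseline Anxiety score" of 11 or more. That measure is a crossing of a cut-off. Without the restriction, everyone already below 11 would count as a success, so it guards against inflation, which is a different problem.
- **PHSS is only a partial precedent.** Its baseline subgroup also serves mean change, percent change and smaller decreases, so it is a severity subgroup rather than an ability-to-respond rule. It does show that the requested form is already in the table.
- **Comparability across instruments is not at stake.** A reader might infer that the rates are meant to be compared with each other. No such comparison is planned, and a common baseline floor would not make different scales comparable.
- **An all-patient rate is legitimate.** It answers how many treated participants improved by 4 points. Mean change, the endpoint that protocol 4.1.2 lists for these scales, is reported in any case.

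It is also true that baseline scores will be summarised with minimum and quartiles (SAP 4.1 and 5). The minimum shows whether anyone starts below 4, but not how many, so a reader could not recover r. That leaves a small, real gap.

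**Conclusion.** The concern holds in a limited form. As written, the DLQI and CDLQI 4-point rates equal r(1 - q), so any participant with a baseline of 0 to 3 is a non-responder by construction. That follows from the denominator rule, the absence of a baseline condition and the scale minimum of 0.

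The size is unknown. It runs from nil at q = 0 to 10.5 points at q = 15% and r = 70%, and every one of these q and r values is an assumption. A single participant could matter for CDLQI if its denominator is small. For POEM the same algebra applies, but the effect is likely negligible.

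The importance is minor. The rates are descriptive additions made in the SAP, and EASI-75 at week 24 is not affected. The documents do not support saying that the rates are in fact biased, nor that the SAP contradicts a rule of its own.

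**What to change.** In the SAP 5.7.2 table, for DLQI and CDLQI, and for POEM for consistency:

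1. Report the 4-point responder rate among participants with a baseline score of 4 or more.
2. State the number with a baseline below 4 for each instrument.
3. Keep the rate over all participants with a value at the visit, labelled as the all-patient rate, alongside.

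This uses data already collected and needs no protocol change. The cost is SAP wording, a slightly smaller denominator for the restricted rate and one extra table line per instrument. If nobody starts below 4, the two rates coincide and the count of zero says so.

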1. INTRODUCTION

Atopic dermatitis (AD), also known as atopic eczema, is a pruritic skin condition characterized by a chronic, relapsing form of skin inflammation. The pathophysiology of AD is complex and is influenced by genetic, immunologic, and environmental factors which lead to a dysfunctional skin barrier and dysregulation of the immune system (Bieber, 2008) (Eichenfield, 2014). Altered epidermal barrier function, together with immune changes in the skin, lead to the development of eczematous lesions with erythema, edema, xerosis, erosions/excoriations, oozing/crusting, and lichenification that may vary by patient age, disease chronicity, as well as race and/or ethnicity.

AD usually presents during early infancy or childhood, though it can persist into or start in adulthood (Kay, 1994). The disease affects 15% to 30% of children and 2% to 10% of adults in industrialized countries, but variation related to geographic region and racial and/or ethnic origin has been described (Bieber, 2008). Population-based studies in the US have demonstrated a higher prevalence of AD in African American children (19.3%) than in European American children (16.1%) (Brunner, 2019) (Kaufman, 2018b) (Kaufman, 2018a) with similar disparities observed in Europe (Alexis, 2019) (Williams, 1995). After adjusting for sociodemographic characteristics, compared to non-Hispanic whites, non-Hispanic blacks were more likely to have incident AD (adjusted odds ratio [aOR] 2.71, 95% confidence interval [CI]: 1.75, 4.19) and both non-Hispanic blacks (aOR 6.26, 95% CI: 2.32, 16.88) and Hispanics (aOR 6.42, 95% CI: 1.93, 21.41) with early childhood AD were more likely to have persistent AD (Kim, 2019). Examining AD severity by self-identified racial subgroups has furthermore suggested greater severity among black children compared to white children by common outcome measures assessing AD signs and symptoms (Ben-Gashir, 2002). In particular, pruritus has been found to have a disproportionate impact on black patients (McColl, 2021) (Whang, 2019). A cross sectional study leveraging the National Ambulatory Medical Care Survey (NAMCS) in the US reported that the numbers of per capita visits for AD among black patients and Asian/Pacific Islanders were 2-fold and 6-fold higher, respectively, compared to whites, suggesting a disproportionate impact on healthcare resource utilization (Janumpally, 2002).

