8.7. Blinding

This is an open-label study, without a reference treatment.

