11. STATISTICAL PLAN

11.1. Statistical Hypothesis

There is no formal statistical hypothesis testing and no planned inferential comparisons in this study.

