11.2. Justification of Sample Size

The enrolled population will attempt to approximate the US census bureau data on proportions of self-reported races that comprise the skin of color population in the United States— to this end all self-reported races representing skin of color will be included, however a cap at approximately 40% will be set for non-black/non-African American participants.

Due to the descriptive character of this study, no formal sample size calculation will be performed. The sample size of this study is chosen empirically to support descriptive analysis of efficacy and safety in the overall skin of color population. With up to a potential 15% drop out rate based on prior studies, 120 participants would yield approximately 105 participants overall.

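### The HADS threshold rates count only falls below 11 among participants selected at 11 or more on one baseline reading, so in a single-arm study part of the apparent remission is regression to the mean

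*SAP*

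**What the plan says.** **HADS.** SAP 5.7.2 lists two threshold analyses: "Percent of patients with Anxiety score < 11 among patients with baseline Anxiety score ≥ 11 at each visit through week 24" and "Percent of patients with Depression score < 11 among patients with baseline Depression score ≥ 11 at each visit through week 24". It lists no reverse transition and no table of HADS categories in all participants. Without any baseline restriction it also plans "Mean and change from baseline in Hospital Anxiety and Depression Scale (HADS) total score, anxiety and depression sub-scores at each visit through week 24". Change from baseline is the HADS endpoint in Protocol 4.1.2; the threshold rates appear only in the SAP.

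**PHSS.** Six responder rates (decreases of at least 1, 2, 3 and 4 points, score 0, and score 0 or 1) are confined to participants with baseline overall severity of 4 or more. No increase rate is planned. Outside that subgroup, SAP 5.7.2 plans mean and percent change and the distribution over grades 0-8 at each visit.

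**Bother items.** For darkening and lightening, the 0-4 distribution is given only for a selected group: "In the subgroup of patients who respond at baseline that they are either" very or extremely bothered (3 or 4). Xerosis has such a subgroup too, but its bother items are also tabulated in everyone with non-zero dryness at baseline.

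**Baseline and design.** Under SAP 6.1, baseline is the last valid value before the first injection. In the Schedule of Events (Table 1), HADS, PHSS and the Dyspigmentation NRS have no screening assessment. Protocol 8.7 states "This is an open-label study, without a reference treatment", and Protocol 11.1 states "There is no formal statistical hypothesis testing and no planned inferential comparisons in this study". The SAP does not mention regression to the mean.

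**The concern.** A participant can score 11 or more at baseline because the underlying level is high, because that week was unusually bad, or both. Selecting on that reading over-represents bad weeks, so some of the selected group will score lower later with no treatment effect. In a stable population, participants who were below 11 and have a bad week later balance those falls, but the plan does not count them.

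A control arm selected in the same way would show how large this effect is. This study has none. Mental health is a secondary objective (Protocol 2.2), and these are the SAP's only HADS threshold results. A statement that a given share of anxious participants fell below the cut-off is easily read as a treatment effect, although its expected value under no effect is well above zero.

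**Working it through.** **The plan's own figure.** Protocol 11.2 says "With up to a potential 15% drop out rate based on prior studies, 120 participants would yield approximately 105 participants overall". The arithmetic is 120 × (1 − 0.15) = 102; 105 would correspond to 12.5% dropout (120 × 0.875 = 105). Neither document gives a figure for the rates at issue. I use 102 only to indicate subgroup size.

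**Inputs.**
- From the documents: HADS subscale range 0-21 and cut-off 11 (SAP 10.3 and 5.7.2); PHSS grades 0-8 and subgroup cut 4 (SAP 5.7.2); bother scale 0-4 and subgroup cut 3 (SAP 5.7.2).
- Assumed, because the documents give none: the mean, SD and baseline-to-visit correlation r of each scale.

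**Method.** Draw baseline X and visit value Y from a bivariate normal with the same mean and SD at both times and correlation r, so there is no true change. Round and clip to the scale; use 2 million draws per setting. Compute P(Y < 11 | X ≥ 11) and P(Y ≥ 11 | X < 11).

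**HADS subscale, SD 4.3**

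| r | Falls below 11, mean 6 | Falls below 11, mean 7 | Falls below 11, mean 8 | Rises to 11 or more, mean 7 |
|---|---|---|---|---|
| 0.9 | 28% | 25% | 22% | 6.5% |
| 0.8 | 39% | 35% | 31% | 9% |
| 0.7 | 48% | 43% | 38% | 11% |
| 0.6 | 55% | 50% | 44% | 13% |

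The two directions cancel in the whole population. At mean 7 and r = 0.7, 20.7% start at 11 or more. Per 120 participants:
- falls: 120 × 0.207 × 0.428 ≈ 10.7
- rises: 120 × 0.793 × 0.113 ≈ 10.7
- net change in the share at 11 or more: zero, while the planned rate reads 43%.

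The subgroup would be small: about 15, 21 or 29 of 102 at means of 6, 7 and 8. With SD 4 and means of 6 to 9 the apparent remission range is 19% to 57%, so the result does not hinge on one choice of SD.

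**PHSS, baseline 4 or more (assumed mean 3.5, SD 1.7)**

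| Rate under no effect | r = 0.9 | 0.8 | 0.7 | 0.6 |
|---|---|---|---|---|
| Decrease ≥ 1 | 34% | 43% | 48% | 52% |
| Increase ≥ 1 (not planned) | 20% | 22% | 23% | 23% |
| Decrease ≥ 2 | 5% | 13% | 20% | 26% |
| Decrease ≥ 3 | 0.2% | 2% | 5% | 9% |

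Decreases of at least 4 points occur in 0% to 2%, score 0 in under 0.5%, and score 0 or 1 in 0% to 3%. At the 1-point cut, the excess of decreases over increases is 34 − 20 = 14 points at r = 0.9 and 52 − 23 = 29 points at r = 0.6; the rest is symmetric noise.

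**Bother items (assumed mean 2 to 2.5, SD 1.2, r 0.6 to 0.9).** Of those at 3-4 at baseline, 14% to 40% are at 0-2 later with no effect. The subgroup starts entirely in the top two categories, so the share there can only stay or fall.

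**The case against.** The study is openly descriptive and single-arm, and the plan does contain results free of this selection. HADS mean change is planned in all participants and is the protocol endpoint; under no effect it stays at zero, so it is a real check on the remission rate. For PHSS, the unselected 0-8 distribution lets a reader see net movement across any grade. Both points stand. A reader might infer that the plan offers nothing to set against the selected rates, and the documents do not support that. The gap that remains is specific to HADS: a mean change cannot show how many participants crossed 11 in each direction.

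A reader might also infer that the bother summaries are one-way improvement rates, or that every PHSS rate is heavily inflated. Neither holds. All five bother categories are tabulated, so a move from 3 to 4 is visible, and the PHSS rates for 3 or more points and for score 0 or 0/1 are little affected.

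Every magnitude rests on assumed inputs. The phrase "characterized by a chronic, relapsing form of skin inflammation" (Protocol 1) describes the skin disease and says nothing about the serial correlation of HADS, while Protocol 3.2.1 expects pigmentation to change slowly, which does not suggest a low correlation for PHSS. That is fair, and it is why ranges are shown. Still, no HADS setting tried gave a negligible rate.

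Finally, everyone is enrolled on high EASI, IGA, BSA and itch (Protocol 7.2.1), so net change in the full analysis set may carry some regression to the mean as well. This also stands: a shift table removes the distortion from selecting on HADS itself, not all of it.

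**Conclusion.** The concern holds for the HADS threshold rates. As planned they would show about 22% to 55% apparent remission with no true change and no net movement (assumed mean 6-8, SD 4.3, correlation 0.6-0.9). It holds in part for PHSS: materially at the 1-point cut (34% to 52% falling against 20% to 23% rising), less at 2 points (5% to 26%), and hardly beyond that (assumed mean 3.5, SD 1.7). For the darkening and lightening bother items, the issue is only that the 0-4 distribution is missing outside the group selected at 3-4.

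The primary endpoint is unaffected. It would go too far to conclude that net threshold change should replace HADS change from baseline as the main HADS result: the latter is the protocol endpoint and is not selected on baseline HADS.

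**What to change.** In SAP 5.7.2:

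1. Add baseline-by-visit shift tables for HADS anxiety and depression, using the bands in SAP 10.3 (0-7, 8-10, 11 or more), in all FAS participants with both values. Report movement in both directions and the net change in the share at 11 or more, next to the existing remission rates.
2. Add PHSS increase rates matching the planned decrease rates.
3. Tabulate the 0-4 darkening and lightening bother items at each visit in all FAS participants, as well as in the selected subgroups.
4. Footnote every rate from a subgroup selected on its own baseline value as including regression to the mean.
5. Keep HADS change from baseline as the main HADS result.

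The cost is a few extra tables from data already collected and a change to SAP wording only. The remission statement will read somewhat less favourably.
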